8.2.2 Primary analysis of the secondary efficacy variables

Binary (responder) variables will be summarized using frequency tables by treatment group for each visit. Continuous variables will be summarized using descriptive statistics by treatment group for each visit. Primary analysis for secondary efficacy variables will be summarized based on imputed data (NRI and MCMC/Monotone Regression for binary and continuous variables, respectively), unless otherwise specified.

8.2.2.1 PASI and IGA responses

For PASI100 response at Week 16 and 24, PASI75 response at Week 4, PASI90 and IGA response at Week 24, the stratified CMH test similar to the primary analysis will be implemented to test for superiority of bimekizumab over adalimumab.

The treatment comparisons at Week 24 for PASI100, PASI90 and IGA will be performed in three different ways using the following randomized treatment arms:

1. Bimekizumab Q4W and bimekizumab Q4W/Q8W combined vs adalimumab (testing H_7 , H_8 and H_9)
2. Bimekizumab Q4W only vs adalimumab (testing H_{10} , H_{11} and H_{12})
3. Bimekizumab Q4W/Q8W vs adalimumab (not part of the hierarchical testing sequence, these analyses will be exploratory and the p-values produced will be nominal)

Because all adalimumab subjects will receive bimekizumab treatment starting at Week 24, inferential comparisons against adalimumab after Week 24 will not be performed. PASI90 and IGA response at Week 56 will be summarized using descriptive statistics only.

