7.2 Treatment(s) to be administered

Unblinded study staff will be responsible for preparation of the clinical study material, including recording the administration information on source documents, and administration of the IMP as sc injections. The unblinded personnel will not be involved in the study in any way other than assuring the medication is taken from the correct kit and administering the IMP to the subjects.

Suitable areas for sc injections are the lateral abdominal wall and upper outer thigh. During each dosing visit, each of the injections should be administered at a separate injection site. Injection sites should be rotated at each visit and injections should not be given into a PSO plaque or areas where the skin is tender, bruised, erythematous, or indurated. The injection should last approximately 10 to 15 seconds.

An IMP Handling Manual will be provided to each site containing instructions regarding drug preparation and dosing.

Eligible subjects will be randomized 1:1:1 to receive the following blinded study treatment regimens: bimekizumab 320mg Q4W throughout the study, bimekizumab 320mg Q4W until Week 16, or adalimumab.

Because of differences in the dosing schedule between bimekizumab and adalimumab and in order to maintain blinding, all subjects will receive 2 injections sc on Weeks 0 (Baseline), 4, 8, 12, 16, 20, and 24, and 1 injection sc in other weeks:

- Subjects randomized to receive bimekizumab 320mg Q4W throughout the study will receive 2 bimekizumab 160mg injections sc Q4W at Weeks 0 (Baseline), 4, 8, 12, 16, 20, 24, 28, 32, 36, 40, 44, 48, and 52. These subjects will receive 1 placebo injection at Weeks 1, 3, 5, 7, 9, 11, 13, 15, 17, 19, 21, and 23.
- Subjects randomized to receive bimekizumab 320mg Q4W/Q8W will receive 2 bimekizumab 160mg injections sc Q4W at Weeks 0 (Baseline), 4, 8, and 12. Subjects will then receive 2 bimekizumab 160mg injections sc Q8W at Weeks 16, 24, 32, 40, and 48. These subjects will receive 1 placebo injection at Weeks 1, 3, 5, 7, 9, 11, 13, 15, 17, 19, 21, and 23, and 2 placebo injections at Weeks 20, 28, 36, 44, and 52.

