2.1.2 Secondary objectives

The secondary objectives of the study are to:

- Evaluate the efficacy of bimekizumab compared to adalimumab after 4, 16, and 24 weeks of treatment
- Evaluate the efficacy of bimekizumab compared to adalimumab at achieving complete clearance according to Psoriasis Area and Severity Index (PASI100) after 16 weeks and 24 weeks of treatment
- Assess the maintenance of efficacy of bimekizumab dosing Q4W versus Q8W at Week 56
- Assess treatment emergent adverse events (TEAEs), serious adverse events (SAEs), and TEAEs leading to withdrawal adjusted by duration of subject exposure to study treatment

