2.4 Determination of sample size

A total of 450 subjects will be randomly assigned in a 1:1:1 ratio to the following treatment groups:

- Bimekizumab 320mg Q4W throughout the study (150 subjects)
- Bimekizumab 320mg Q4W/Q8W (ie, bimekizumab 320mg Q4W until Week 16, then bimekizumab 320mg Q8W from Week 16 through Week 52 (150 subjects)
- Adalimumab 80mg administered as an initial dose, followed by 40mg Q2W starting 1 week after the initial dose (ie, adalimumab will be administered according to the labeling recommendations) until Week 24, then bimekizumab 320mg Q4W from Week 24 to Week 52 (150 subjects)

When comparing bimekizumab to adalimumab, the assumed responder rates for PASI90 and IGA at Week 16 for the bimekizumab group are 75% and 85%, respectively. These estimates are based on the results of the Phase 2b PS0010 study. The PASI90 responder rates at Week 16 for adalimumab from the VOYAGE-1 and VOYAGE-2 studies were 50% and 47%, respectively (Blauvelt et al, 2017; Reich et al, 2017). Additionally, the IGA responder rates at Week 16 for adalimumab in VOYAGE-1 and VOYAGE-2 were 66% and 68%, respectively. For the purposes of these sample size calculations at Week 16, we assume a PASI90 responder rate and IGA responder rate for adalimumab of 50% and 68%, respectively.

The testing procedure described in protocol Section 14.3 indicates that the first test will be to demonstrate noninferiority to adalimumab for the co-primary variables of PASI90 and IGA at Week 16. If non-inferiority for both tests is demonstrated, then superiority to adalimumab will be tested.

Because the superiority evaluation is the more stringent test, sample size calculations are based on the testing of superiority to adalimumab for PASI90 and IGA at Week 16. Given these assumptions and a sample size of 150 subjects in the adalimumab arm and 300 subjects in the pooled bimekizumab arms, the power to detect a statistically significant difference between bimekizumab and adalimumab is >99% for PASI90 response and 97% for IGA response. This

assumes a 2-sided significance level of 0.05. Because both co-primary endpoints are highly powered independently, and because PASI and IGA response tend to be highly correlated, the overall power for achieving superiority on both co-primary endpoints is not calculated here.

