4.5 Multiple comparisons/multiplicity

[figure not shown]
The statistical analysis of the co-primary efficacy variables and selected secondary efficacy variables will account for multiplicity and control the familywise Type I error rate at a 2-sided alpha level of 0.05 by using a fixed sequence testing procedure.

The hypotheses (H_1 , H_2 , H_3 , H_4 , H_5 , H_6 , H_7 , H_8 , H_9 , H_{10} , H_{11} and H_{12}) comparing bimekizumab vs. adalimumab will be tested at a 2-sided alpha level of 0.05.

The first 2 hypotheses (H_1 and H_2) will test whether bimekizumab is noninferior to adalimumab for the co-primary efficacy variables, PASI90 response at Week 16 and IGA response at Week 16. This evaluation of noninferiority will be tested at a 1-sided alpha level of 0.025 and will be based on a 1-sided 97.5% CI and a noninferiority margin of 10%. If noninferiority is achieved, the alpha will be passed to the next test in the sequence, allowing the testing procedure to proceed. The co-primary efficacy variables of PASI90 response at Week 16 and IGA response at Week 16 will then be evaluated for superiority relative to adalimumab at a 2-sided alpha level of 0.05, and testing will proceed only if superiority is achieved for both endpoints.

The hypotheses associated with the subsequent secondary efficacy endpoints are based on testing for superiority relative to adalimumab. See Figure 4-1 for details on this procedure.

Figure 4-1: Sequence of testing

Note: Calculations for H₁-H₉ are based on the combined Bimekizumab arms with the sample size of 300. * in H₁₀-H₁₂ indicated calculations are based on the Bimekizumab Q4W/Q4W arm only with sample size of 150.

BKZ=bimekizumab; H=hypothesis; IGA=Investigator's Global Assessment; PASI=Psoriasis Area Severity Index; Q4W=every 4 weeks

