8 EFFICACY ANALYSES

All efficacy analyses will be performed on the RS unless otherwise specified.

For efficacy endpoints tested through initial treatment period, comparisons will be made between BKZ Total (pooling the two identical treatment arms prior to week 16) and ADA treatment groups.

For by visit summaries, results will be presented by each individual treatment group as well as BKZ Total group (BKZ 320mg Q4W and BKZ 320mg Q4W/Q8W combined). Change from Baseline will be summarized through initial and maintenance treatment period for BKZ treatment groups; while for the ADA group, the change from baseline will only be summarized up to Week 24.

Additional summaries through the initial and maintenance treatment period will be produced for subjects who received bimekizumab from Week 24 onwards (BKZ week 24 set) in all three randomized treatment groups.

In addition, for subjects who started with adalimumab and switched treatment at the Week 24 Visit, change from Baseline (at Week 24) will be evaluated from Week 28 to Week 56 for PASI score and DLQI score only (see Section 3.2).

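### At Week 24 the controlled tests cover the pooled bimekizumab arms and Q4W alone; Q4W/Q8W versus adalimumab stays nominal, so a pooled success does not establish superiority for that regimen

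*SAP*

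**What the plan says.** SAP 2.1.2 sets the secondary objective: "Evaluate the efficacy of bimekizumab compared to adalimumab after 4, 16, and 24 weeks of treatment". It names no regimen.

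SAP 4.5 undertakes to "control the familywise Type I error rate at a 2-sided alpha level of 0.05 by using a fixed sequence testing procedure". The note to Figure 4-1 says that H1-H9 "are based on the combined Bimekizumab arms with the sample size of 300", and that H10-H12 use the Q4W arm only, with 150 subjects. SAP 8.2.2.1 makes three Week 24 comparisons with adalimumab for PASI100, PASI90 and IGA: the combined arms (H7-H9), Q4W alone (H10-H12), and a third described as "Bimekizumab Q4W/Q8W vs adalimumab (not part of the hierarchical testing sequence, these analyses will be exploratory", with nominal p-values. Protocol 14.3.2.1.2 lists only the first two. SAP 8.2.2.1 also rules out inferential comparison with adalimumab after Week 24, because those subjects then switch to bimekizumab. Week 56 is descriptive.

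On pooling, SAP 8 explains the combined group for the initial period as "pooling the two identical treatment arms prior to week 16". On dosing, Protocol 7.2 says of the Q4W/Q8W arm: "Subjects will then receive 2 bimekizumab 160mg injections sc Q8W at Weeks 16, 24, 32, 40, and 48". At Week 20 that arm has two placebo injections, while the Q4W arm has two bimekizumab injections. Protocol 5.6 places assessments before dosing at every visit.

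**The concern.** The reason given for pooling stops applying before Week 24. At the pre-dose Week 24 assessment the Q4W arm is 4 weeks from its last active dose and the Q4W/Q8W arm is 8 weeks from it. H7-H9 therefore test a 1:1 mixture of two regimens, and a strong Q4W result can carry the mixture.

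H10-H12 resolve this for Q4W. For Q4W/Q8W the matching comparison is pre-specified but has no place in the sequence, and Week 24 is the last point at which adalimumab is available as a comparator. The stake is attribution: a statement that bimekizumab was superior at Week 24 may be read as covering both regimens, while only the pool and Q4W have error-controlled evidence.

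**Working it through.** **Inputs.** SAP 2.4 gives "a sample size of 150 subjects in the adalimumab arm and 300 subjects in the pooled bimekizumab arms" and states that "the assumed responder rates for PASI90 and IGA at Week 16 for the bimekizumab group are 75% and 85%, respectively". The adalimumab planning rates are 50% and 68%. The documents give no Week 24 rate and no PASI100 rate. I assume that the Week 16 rates hold at Week 24 for Q4W and adalimumab, and I vary the share of the advantage that Q4W/Q8W keeps.

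**Formula.** Two proportions, normal approximation, two-sided 0.05:
- p̄ = (n_A·p_A + n_B·p_B)/(n_A + n_B)
- SE0 = √[p̄(1−p̄)(1/n_A + 1/n_B)]
- SE1 = √[p_A(1−p_A)/n_A + p_B(1−p_B)/n_B]
- power = Φ[(p_B − p_A − 1.96·SE0)/SE1]

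**The plan's own figure.** With 150 versus 300:
- PASI90 50% v 75%: p̄ = 0.667, SE0 = 0.0471, SE1 = 0.0479, z = 3.29, power 99.95% (stated: above 99%).
- IGA 68% v 85%: p̄ = 0.793, SE0 = 0.0405, SE1 = 0.0433, z = 2.09, power 98.2%. It is 97.5% with unpooled variance and 97.6% with a continuity correction (stated: 97%).

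The SAP figures are reproduced closely enough to use the same method here.

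**Week 24, worked case: Q4W/Q8W keeps half the advantage.**
- PASI90: the Q4W/Q8W rate is 50 + 12.5 = 62.5%, and the pooled rate is (75 + 62.5)/2 = 68.75%.
  - Pooled, 150 v 300: (0.1875 − 1.96×0.0484)/0.0488 = 1.90, power 97%.
  - Alone, 150 v 150: (0.125 − 1.96×0.0573)/0.0568 = 0.22, power 59%.
- IGA: the Q4W/Q8W rate is 68 + 8.5 = 76.5%, and the pooled rate is (85 + 76.5)/2 = 80.75%.
  - Pooled: (0.1275 − 1.96×0.0424)/0.0444 = 1.00, power 84%.
  - Alone: (0.085 − 1.96×0.0517)/0.0515 = −0.32, power 38%.

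**Range.** The last column comes from 200,000 simulated trials with an unstratified z-test.

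| Endpoint | Advantage kept | Q4W/Q8W rate | Pooled rate | Pooled test significant | Q4W/Q8W alone significant | Pooled yes, alone no |
|---|---|---|---|---|---|---|
| PASI90 | all | 75% | 75% | >99% | 99.5% | <1% |
| PASI90 | 90% | 72.5% | 73.75% | >99% | 98% | 2% |
| PASI90 | half | 62.5% | 68.75% | 97% | 59% | 37% |
| PASI90 | none | 50% | 62.5% | 72% | 2.5% | 69% |
| IGA | all | 85% | 85% | 98% | 94% | 4% |
| IGA | 90% | 83.3% | 84.15% | 97% | 87% | 10% |
| IGA | half | 76.5% | 80.75% | 84% | 38% | 47% |
| IGA | none | 68% | 76.5% | 49% | 2.5% | 46% |

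These are powers for each test taken by itself; they do not include the chance that the sequence stops earlier. In the no-advantage row, both pooled tests succeed together in about 34% to 43% of simulated trials, for a latent correlation between the endpoints of 0 to 0.9.

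**The case against.** The plan sees the issue and handles most of it. Protocol 14.3.2.1.2 splits the Week 24 comparisons precisely to separate subjects staying on Q4W from those moving to Q8W. Q4W has its own controlled tests. The Q4W/Q8W comparison is pre-specified with the same stratified CMH test and openly labelled exploratory, and by-visit results are shown for each arm. A failure of Q4W/Q8W at Week 24 would therefore be visible. All of that stands; what is missing is confirmatory status for one comparison.

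A reader might infer three stronger things that the documents do not support.
- **That familywise error is uncontrolled.** It is controlled for H1-H12 as defined, and the figure note says plainly that H7-H9 concern the combined arms.
- **That a stated objective goes unanswered.** The Week 24 objective names no regimen, and the Q4W versus Q8W question is assigned to Week 56.
- **That the trial is likely to declare success with an ineffective Q4W/Q8W regimen.** Both arms receive active drug at Week 16, so one planned dose separates them at the Week 24 assessment. Protocol 2.2.1.1 reports a median half-life of about 28 days in healthy subjects. Losing the whole 25- or 17-point advantage after one omitted dose is a boundary case. The documents contain no exposure-response data that would exclude it, so the 72% and 49% figures show what is possible, not what is expected.

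**Conclusion.** The point holds as a cheap improvement to a late secondary family; the co-primary conclusions are untouched. A positive H7-H9 supports a claim about the mixture of two regimens. It does not establish superiority of Q4W/Q8W over adalimumab, and no controlled test in the plan does.

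The size depends on how much of its advantage Q4W/Q8W keeps. At 90% the pooled and single-arm answers disagree in only about 2% (PASI90) and 10% (IGA) of trials. At half, the pooled test succeeds in 97% and 84% while Q4W/Q8W alone succeeds in 59% and 38%. With the full advantage, the arm's own test has 99.5% and 94% power, so a controlled test would very probably succeed if the regimen performs as planned. These figures rest on carrying Week 16 planning rates to Week 24 and on an unstratified approximation. Nothing can be computed for PASI100. The order within H7-H12 is in a figure that is not reproduced in the text, but the argument does not depend on it.

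**What to change.** Before unblinding (the documents do not give that date):

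1. Append H13, H14 and H15 after H12: Q4W/Q8W versus adalimumab at Week 24 for PASI100, PASI90 and IGA, in a stated order. Test each at two-sided 0.05 only if every preceding hypothesis has been rejected, including the previous one of these three. Making all three conditional on H12 alone would allow three parallel tests at full alpha.
2. Use the stratified CMH analysis with nonresponder imputation already planned for the third comparison in SAP 8.2.2.1.
3. State that the sensitivity analysis in SAP 8.2.3, which excludes the approximately 24 subjects given incorrect placebo or active treatment at Visit 20, also applies to H13-H15. If Visit 20 means Week 20 (an assumption), that error falls on the one dose separating the arms.
4. State that H7-H9 support a claim about the pooled arms only. This sentence is worth adding even if the sponsor declines H13-H15.
5. Update SAP 4.5, Figure 4-1 and 8.2.2.1. Align Protocol 14.2, Figure 14-1 and 14.3.2.1.2 by amendment, or list the change in SAP 3.10.

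The cost is minor document work, with no new subjects, visits or data. Tests at the end of a fixed sequence take no alpha or power from H1-H12. The one real downside is that a failed H13, H14 or H15 must be reported as a failure.

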8.2.3 Sensitivity analyses of the secondary efficacy variables

For binary response variables (PASI100 at Week 16 and 24, PASI75 at Week 4, PASI90 at Weeks 24 and 56, and IGA at Weeks 24 and 56), sensitivity analyses #1 and #2 (Section 8.1.3.1 and Section 8.1.3.2) will be performed. For PASI90 and IGA at Week 56, the sensitivity analyses are used to impute missing data for descriptive summaries only. Details regarding missing data algorithm can be found in Section 4.2.1.6.

It was noted during the conduct of the study that approximately 24 subjects received incorrect Placebo/Active treatment at Visit 20. All subsequent treatments were administered per protocol. The main analyses of the endpoints at Week 24 will include all subjects in the RS, however the potential impact of this on the Week 24 secondary endpoints (PASI90, PASI100 and IGA response) will be assessed through sensitivity analyses excluding these subjects from the analysis population.

8.3 Statistical analysis of other efficacy variables

The other efficacy variables are listed below and will be evaluated according to the planned assessments in the protocol, this excludes the timepoints for the primary and secondary variables specified above in Section 8.1.1 and Section 8.2.1.

Binary (responder) variables will be summarized using frequency tables by treatment group for each visit. Continuous variables will be summarized using descriptive statistics by treatment group for each visit. All variables will be summarized based on imputed data (NRI and MCMC/Monotone Regression for binary and continuous variables, respectively), unless otherwise specified.

For variables that are part of the sequence testing procedure, summaries based on observed case data will also be provided. There may be cases where the multiple imputation model fails to converge. In such situations, the last observation carried forward (LOCF) approach will instead be used to impute the missing data.

By visit summaries will include the bimekizumab and adalimumab treatment groups. There will be some key approaches for understanding the data after Week 24:

- Summary of data for the RS through initial and maintenance treatment period based on randomized treatment group including bimekizumab Q4W, bimekizumab Q4W/Q8W and bimekizumab total. The adalimumab group will only be summarized up to Week 24
- Summaries through the initial and maintenance treatment period for subjects who received bimekizumab from Week 24 onwards (BKZ week 24 set) in all three randomized treatment groups.
- For subjects who started with adalimumab and switched treatment at the Week 24 Visit, change from Baseline (at Week 24) will be evaluated from Week 28 to Week 56 for PASI score and DLQI score only (see Section 3.2).
- Summary of Maintenance treatment period data among responders only for PASI90, PASI100, IGA (0/1), and DLQI respectively;
 - For Week 16 responders in bimekizumab Q4W, bimekizumab Q8W and bimekizumab total (Maintenance Set)
 - For Week 24 responders in ADA/BKZ arm (Bimekizumab Set)

No adjustments to the analysis sets will be made for the subjects who were incorrectly dosed (see Section 8.2.3)

8.3.1 PASI

8.3.1.1 PASI50, PASI75, PASI90 and PASI100 response rate

Categorical response variables, PASI50, PASI75, PASI90 and PASI100 over time are defined to be equal to 1 if the percentage improvement from Baseline to visit timepoint in the PASI scores is 50%, 75%, 90% and 100% respectively or greater and 0 if the percentage improvement from Baseline to visit timepoint is less than 50%, 75%, 90% and 100% respectively. This definition is introduced for the purpose of identifying subjects who respond to the treatment (1 = responder, 0 = non-responder). The definition of PASI score percentage improvement from Baseline is given in Section 8.1.1.1.

A line plot of the PASI responder (PASI50, PASI75, PASI90, and PASI100) rate over time, by treatment group will be produced.

8.3.1.2 Time to PASI50, PASI75, PASI90 and PASI100 response through initial treatment period and through Week 24

Time to PASI50, PASI75, PASI90, and PASI100 response (in days) during the Initial Treatment Period will each be calculated as:

Min (Date of first PASI_{xx} response, Date of Week 16 visit) – Date of Baseline visit + 1, here xx represents 50, 75, 90, 100 respectively.

All visits up to and including Week 16 (including unscheduled visits) will be considered.

For the PASI response through initial treatment period variables, subjects who discontinue study treatment without achieving a given PASI response prior to Week 16 visit will be censored at the date of the last observed PASI assessment on or prior to the date of study treatment

discontinuation. Subjects who reach the Week 16 Visit without achieving the given response will be censored at the date of the last observed PASI assessment on or prior to Week 16 Visit.

Subject will be censored at baseline (Day 0) if there is no Baseline PASI assessment or no post Baseline PASI assessment.

For the PASI response through Week 24 variables, data will be censored in the same manner as Week 16 initial treatment period variables.

Time to PASI50, PASI75, PASI90, and PASI100 response will each be estimated and presented using the Kaplan-Meier product-limit method for each treatment group.

Kaplan-Meier plots of time to PASI responses will also be presented by treatment group. In these Kaplan-Meier plots, the line will start at 0 (since there are no responders at Week 0) and will increase over time, representing time to achieving the response.

The median time to response, including the two-sided 95% confidence interval, will be calculated for each treatment. Comparisons of all bimekizumab vs adalimumab will be analyzed using a log-rank test stratified by region and prior biologic exposure.

